9.2.1 Primary endpoint

The primary endpoint is **Technical success**. This endpoint is measured at exit from the catheterization laboratory. All of the following must be present:

- Alive
- Successful delivery of the TCD, and retrieval of the TCD delivery system
- Deployment and correct positioning of a single intended TCD. Repositioning and recapture of the device, if needed, is not classified as failure.
- No additional unplanned or emergency surgery or re-intervention related to the TCD or delivery system
- Adjunctive balloon aortic tamponade is permissible and consistent with technical success

9.2.2 Secondary endpoint: Closure success

This secondary endpoint is a composite of the primary endpoint and hemostasis of the trans caval aortic access site. This endpoint is measured at exit from the catheterization laboratory. All of the following must be present:

- Alive
- Successful delivery of the TCD, and retrieval of the TCD delivery system
- Deployment and correct positioning of a single intended TCD. Repositioning and recapture of the device, if needed, is not classified as failure.
- No additional unplanned or emergency surgery or re-intervention related to the TCD or delivery system. Adjunctive balloon aortic tamponade is permissible and consistent with technical success
- Complete occlusion of the aortocaval fistula on the completion aortogram.

9.2.3 Secondary endpoint: Device Success

A key performance endpoint is **Device success**. This endpoint is measured at 30 days and 12-months. All of the following must be present

- Alive
- Original intended TCD in place
- No additional surgical or interventional procedures related to access or the device after exit from the cath lab
- Intended performance of the TCD, including all of

- Structural Performance: No migration, embolization, detachment, fracture, hemolysis, or endarteritis related to the TCD
- Hemodynamic performance: No abdominal aortic obstruction caused by the TCD implant
- Absence of para-device complications (large retroperitoneal hematoma, pseudoaneurysm, distal thromboembolism, or pulmonary thromboembolism)

9.2.4 Secondary endpoint: Procedural Success

The primary safety endpoint is **Procedural success**. This endpoint is measured at 30 days. All of the following must be present

- Device success
- No device-related Serious Adverse Events, defined as VARC-2 life-threatening bleeding, major vascular or cardiac complications related to the TCD requiring unplanned reintervention or surgery (such as covered stent implantation at the trans caval access site).

9.2.5 Additional Secondary Endpoints

Additional secondary endpoints include

- Procedure success classifying covered stent implantation as a normal provisional part of the procedure.
- Covered stent implantation at the TCD implantation site
- Acute aorto-caval fistula score at procedure completion ¹²: 0=occlusion, 1=patent fistula, 2=cruciform fistula pattern, 3=extravasation.
- Modified VARC-2 vascular complications ¹² at 30 days
- VARC-2 bleeding complications ¹² at 30 days
- Major adverse cardiovascular events (MACE), defined as VARC-2 Early Safety composite: No mortality, stroke, life-threatening bleeding, AKI stage 2+, major vascular complication, valve-related complication
- Closure success at 30 days and 12 months.
- Mortality, all-cause, cardiovascular vs non-cardiovascular, peri- vs non-periprocedural, related to TCD or not)
- Aorto-caval fistula patency at each timepoint, assessed combining completion angiography and arterial-phase follow-up CT.
- AKIN acute kidney injury
- Freedom from infection related to the TCD at each time point
- Thrombocytopenia < 50,000 attributable to residual aorto-caval fistula or the TCD
- Hemolysis attributable to residual aorto-caval fistula or the TCD
- CT analysis: Device position; Device integrity; Aortocaval fistula patency; Aortocaval tract pseudoaneurysm; Aortic pseudoaneurysm; Retroperitoneal hematoma grade (stranding {=absent and not

- evidence of overt bleeding; } small; moderate; larger); Intracaval mass or thrombus; Aortic dissection and inferred relatedness to TCD (adjacent to access port) or procedure (remote to access port)
- Outcomes of subjects greater than 65 years (i.e. eligible for Medicare based on age), to determine generalizability to the Medicare population¹

9.2.6 Independent Clinical Events Adjudication

An independent Clinical Events Adjudication Committee will review all of the following that occur in the first year. The CEAC adjudication will be performed after 30-day and after 12-month data are collected. The CEAC will rely on independently-monitored data collected in the electronic case report forms, with additional source document review upon request. The adjudicated endpoints will include:

- Deaths
- Primary endpoint (technical success) and key secondary endpoints (device success, procedure success)
- Modified VARC-2 vascular complications
- VARC-2 bleeding complications
- Major adverse cardiovascular events (MACE), defined as VARC-2 Early Safety composite: No mortality, stroke, life-threatening bleeding, AKI stage 2+, major vascular complication, valve-related complication

The CEAC will classify relatedness of the above events to the TCD device.

9.3 Core Laboratory

The NHLBI CT core laboratory will analyze follow-up CT scans in comparison with baseline. Analysis will include

- TCD position
- TCD integrity
- Aortocaval fistula patency
- Aortocaval tract pseudoaneurysm
- Aortic pseudoaneurysm
- Retroperitoneal hematoma grade (stranding {=absent and not evidence of overt bleeding}; small; moderate; large)
- Intracaval mass or thrombus
- Aortic dissection and inferred relatedness to TCD (adjacent to access port) or procedure (remote to access port)

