10.0 ADVERSE EVENT REPORTING

10.1 Definitions

Adverse events: Any untoward medical occurrence in a human subject, including any abnormal sign (e.g., abnormal physical exam or laboratory finding), symptom, or disease, temporally associated with the subject's participation in the research, whether or not considered related to the subject's participation in the research.

This will include:

- Expected events related to the subject's disease process during active enrollment in the research protocol and do not directly result from use of the investigational device or study.
- Procedural events directly related to the cardiac catheterization procedure and recovery from the procedure and do not directly result from use of the investigational device.

Serious Adverse Event (SAE): A serious adverse event that results in any of the following and NOT directly related to the device. This includes any event that

- Results in death
- Is life-threatening (places the subject at immediate risk of death from the event as it occurs);
- results in in-patient hospitalization or prolongation of existing hospitalization;
- results in a persistent or significant incapacity;
- results in a congenital anomaly/birth defect (not relevant to this study) ;
- that may not result in death, be life-threatening, or require hospitalization may be considered serious when, based upon appropriate medical judgment, they may jeopardize the patient ("important medical event); or
- based upon appropriate medical judgment, may jeopardize the subject's health and may require medical or surgical intervention to prevent one of the other outcomes listed in this definition.

Adverse Device Effect (ADE): Any untoward or unintended response to a medical device. This definition includes any event resulting from insufficiencies or inadequacies in the instructions for use or the deployment of the device or any event that is a result of user error.

During this clinical investigation, an event should be considered related to the TCD when it is the result of:

- Delivery and implantation of the TCD
- Retrieval of the TCD delivery system
- Adjunctive balloon aortic tamponade if performed

An event will be considered NOT related to the TCD when it is the result of:

- A pre-existing medical condition
- Clearly attributable to TAVR or to trans caval aortic access before undertaking trans caval site closure (example: paravalvular leak or trans caval guidewire crossing)

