10.2.2 Attribution of adverse events to the research protocol

The relatedness of adverse events will be classified as:

Classification	Description
Definite	The event is clearly related to the research protocol.
Probable	The event is likely related to the research protocol. The event has a reasonable temporal relationship to the research device or research procedure and alternative causes, such as underlying disease, concomitant medications, or concomitant treatment-can be excluded.
Possible	The event may be related to the research protocol. The event has a reasonable temporal relationship to the research device or research procedure, and attribution of the event to the device or procedure cannot be excluded. However, alternative causes—such as underlying disease, concomitant medications, or concomitant treatments—are presumably responsible.
Unlikely	It is doubtful the event is related to the research protocol. The event can reasonably be explained by other factors, including underlying disease, concomitant medications, or concomitant treatments.
Unrelated	The event is clearly not related to the research protocol. There either is no temporal association with the research device or procedure, or the event is readily explained by other factors, including underlying disease, concomitant medications, or concomitant treatments.

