Aortic or other vascular injury such as aortic dissection, pseudoaneurysm or perforation	Heavily diseased aortas may be injured during caval-aortic crossing or during closure device deployment	2	4	8	The TCD Implant and delivery system are designed to overcome challenges associated with off-label use of commercially-available devices. Iatrogenic aortic pseudoaneurysm is part of the spectrum of retroperitoneal hemorrhage, and represents a volume of blood in continuity with the aorta that is partly or completely surrounded by fresh or organized thrombus. We expect the pseudoaneurysm and hematoma, both in physical proximity to the implanted TCD, to resolve in follow-up as part of healing.	The risk is rated as tolerable. It is considered justified in light of the potential benefit. Risk will be further mitigated by monitoring of subjects for signs and symptoms of blood loss to allow for early treatment. The clinical protocol will instruct physicians to use either balloon aortic tamponade or a covered stent in the case of aortic injury. The protocol will include CT examinations at each follow up through 1 year to monitor vascular injury.
Thrombocytopenia or hemolytic anemia as a consequence of aorto-caval fistula	Mechanical injury to blood cells may result from residual aorto-caval shunt after device closure of the caval-aortic access site	1	3	3	Animal testing with the TCD demonstrated immediate hemostasis. The TCD was specifically designed to overcome challenges associated with off-label use of commercially-available devices.	The risk is rated as negligible. It is considered justified in light of the potential benefit. Risk will be further mitigated by monitoring of subjects for signs and symptoms of blood loss to allow for early treatment. The clinical protocol will instruct physicians to use either balloon aortic tamponade or a covered stent in the case of aortic injury. The protocol will include CT examinations at each follow up through 1 year to monitor vascular injury.

KEY LEVEL	1	2	3	4	5
Probability	Rare	Uncommon	Common	Normal	
Severity	Easy to correct, no anticipated harm to patient	Difficult to correct, no anticipated harm to patient	Potentially harmful to patient	Likely harmful, even with immediate correction	Life threatening
Risk Score	1-4	5-9	10-20	>20	
Risk Interpretation	Negligible	Tolerable	Tolerable but undesirable	Intolerable	

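### Aortic dissection is attributed to the TCD by location in 9.2.5 and 9.3 but by cause in 10.1, and 9.2.6 does not say which rule the adjudicators use

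*Combined protocol and SAP*

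**What the plan says.** **Location rule.** Section 9.3 lists among the core-laboratory CT readings "Aortic dissection and inferred relatedness to TCD (adjacent to access port) or procedure (remote to access port". Section 9.2.5 repeats the item within the CT analysis, so it is also a secondary endpoint.

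**Cause rule.** Section 10.1 says that, in this investigation, "an event should be considered related to the TCD when it is the result of" TCD delivery and implantation, retrieval of its delivery system, or "Adjunctive balloon aortic tamponade if performed". Among the events that are not TCD-related it lists those "Clearly attributable to TAVR or to trans caval aortic access before undertaking trans caval site closure", and gives guidewire crossing as an example. Section 10.1 also names aortic dissection among the anticipated adverse device effects, so both rules deal with this event.

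**Adjudication.** Section 9.2.6 says "The CEAC will classify relatedness of the above events to the TCD device". It cites neither rule and does not say how the core laboratory's inference is to be used.

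**Risk analysis.** On aortic and other vascular injury, Appendix A says "Heavily diseased aortas may be injured during caval-aortic crossing or during closure device deployment".

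**The concern.** The access port is not made by the TCD. By the procedure in 5.3, an electrified guidewire and then the valve introducer sheath open it, the valve is implanted, and only then is the TCD brought in. Injury next to the port may therefore come from crossing or from closure. Conversely, a tamponade balloon or the TCD delivery system may injure the aorta away from the port. Location is evidence about cause but does not settle it.

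At stake is whether a dissection in a first-in-human device study is reported as due to the device. As written, the CT endpoint can charge the TCD with an access injury or clear it of an injury that 10.1 assigns to it. A reader could also find the opposite answer for the same subject in the adjudicated results. Nothing in the plan says which would prevail.

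**Working it through.** The plan gives no figure to reproduce on this point. The check is to run the two rules over the possible combinations of location and cause.

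| Dissection | 9.2.5 / 9.3 (location) | 10.1 (cause) | Agree? |
|---|---|---|---|
| Beside the port, clearly from guidewire crossing | TCD | Not TCD-related | No |
| Beside the port, from TCD deployment | TCD | TCD-related | Yes |
| Remote, from balloon tamponade or TCD delivery | Procedure | TCD-related | No |
| Remote, clearly from the valve procedure | Procedure | Not TCD-related | Yes |
| Beside the port, cause unclear | TCD | Settled by neither list | Open |

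The first row over-attributes to the TCD relative to 10.1, and the third under-attributes. The errors run in both directions, so no constant correction would reconcile the two results. Appendix A foresees both crossing and closure as causes, so the first row is not a remote hypothetical.

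Next, does another section break the tie? Section 9.2.6 assigns the call to the CEAC but names no definition. The five-level scale in 10.2.2 has the research protocol as its target (its top level reads "The event is clearly related to the research protocol") and treats device and procedure together. It cannot supply a TCD-specific answer.

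Size, taking the 15 treated subjects of 9.1 as denominator:

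- One reassigned case: 1/15 = 6.7 percentage points.
- No TCD-related dissection: 0/15 = 0%, exact (Clopper-Pearson) 95% interval 0 to 21.8%. The upper limit is 1 − 0.025^(1/15) = 0.218.
- One TCD-related dissection: 1/15 = 6.7%, exact 95% interval 0.2 to 31.9%. The lower limit is 1 − 0.975^(1/15) = 0.0017, and the upper is the 97.5th percentile of Beta(2, 14), 0.319.

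Follow-up CT is done only when renal function permits (5.3). If fewer than 15 are scanned, one case weighs more in the CT table.

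Reach into other endpoints:

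- Technical success (9.2.1) is measured at exit from the catheterization laboratory and does not use the CT rule.
- Device success (9.2.3) does not list dissection, and its reintervention criterion covers both access and device.
- The stopping rule (9.4.1) counts deaths within 30 days whatever their cause.

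**The case against.** The strongest reply is that the conflict is small and mostly resolved in practice. The location rule concerns a single CT finding and calls itself an inference. Section 10.1 is worded for the whole investigation, so it is the natural default for the CEAC. It also excludes only events clearly due to earlier access, so the first conflict arises only when crossing is clearly the cause. The analysis is descriptive, with no acceptance criterion (9.2). All of this stands and limits the point. It does not remove it: the CT attribution is itself a listed endpoint, and 9.2.6 does not adopt 10.1.

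A reader might infer more than the documents support:

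- **That 10.2.2 contradicts 10.1.** It does not. It grades relation to the research protocol, so an event can be definite there and still not TCD-related. The fair criticism is only that the scale cannot isolate the TCD.
- **That Procedural success turns on the CT rule.** Section 9.2.4 does not use it. The endpoint is adjudicated, and its TCD-related vascular part requires unplanned reintervention or surgery.
- **That Appendix A gives the chance of a discordant case.** Its row pools dissection with pseudoaneurysm, perforation and other vascular injury, and grades probability in words. No frequency of discordant dissections follows from it.
- **That the CEAC list is deficient because some attribution-defined endpoints, such as TCD infection and thrombocytopenia, are not on it by name.** Section 9.2 sends only key events to independent adjudication, and which events are key is a choice. Hemolysis and endarteritis already reach the CEAC through Device success.

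**Conclusion.** The point holds for aortic dissection. The location rule and the cause rule can assign the same lesion oppositely, in both directions, and the plan does not say which governs. The consequence is a possible disagreement between the CT secondary endpoint and the adjudicated result, at 6.7 percentage points per case in 15. The primary endpoint and the stopping rule are unaffected.

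This rests on two assumptions: that 15 is the denominator, and that a dissection reaches the CEAC as a vascular complication under 9.2.6 (the documents cite the modified VARC-2 definitions but do not reproduce them). How often a discordant case would occur cannot be estimated from the documents. The correction is worth making because it is cheap and concerns a device-safety attribution, not because any main conclusion depends on it.

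**What to change.** 1. In 9.2.5 and 9.3, delete the inferred relatedness and have the core laboratory report only whether a dissection is adjacent to or remote from the port.
2. In 9.2.6, state that the CEAC classifies TCD-relatedness by the cause rule in 10.1, using all available procedural and imaging records, with CT location as one input.
3. State that the 10.2.2 scale is not the TCD-relatedness call, because it pools device and procedure.

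The CEAC should not be told to rely on comparing angiograms before and after TCD release. Section 5.3 describes aortography before crossing and then an angiogram once the aortic disc is against the wall, with none described between crossing and exposure of the disc. Those images cannot by themselves separate crossing injury from TCD delivery injury. Some cases will remain a matter of judgement under 10.1.

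The cost is wording in the protocol, the case report form and the CEAC charter. No visit, scan, subject or committee is added.

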9.4 Data Safety Monitoring

A Data Safety and Monitoring Board (DSMB) appointed by the NHLBI Division of Intramural Research will monitor the safety of subjects in the study as described in the investigational plan. All members of the

¹ Guidance for the Public, Industry, and CMS Staff Coverage with Evidence Development Document Issued on November 20, 2014, <https://www.cms.gov/medicare-coverage-database/details/medicare-coverage-document-details.aspx?MCDId=27>

DSMB are unaffiliated to the study. The NHLBI DSMB will review the protocol progress report at six month intervals. The DSMB may recommend early termination of the study for considerations of safety and efficacy. Unanticipated Adverse Device Effects (UADEs) will be submitted to the DSMB following the same timelines as the IRB (See section 10.2.4).

In the case of death or serious UADE, if the sponsor and the principal investigator determine that the event presents an unreasonable risk to the participating subjects, the clinical trial will be terminated within 5 working days after making that determination and not later than 15 working days after the sponsor first receives notice of the effect. [21 CFR 812.46]. All clinical sites will be notified of this action.

Each institutional IRB will review all Serious Adverse Events, Unanticipated Adverse Device Effects, and Unanticipated Problems, and may choose to suspend or terminate the protocol based on those findings. We believe this will protect subject safety.

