9.4.1 Stopping Rules

The study will be monitored to ensure that the mortality within 30-days after the procedure does not substantially exceed an anticipated rate. We anticipate the rate of 30-day mortality is 10% or less and determine the stopping rule by a Bayesian approach ¹³. The stopping boundary is reached if the posterior probability that the 30-day mortality rate exceeds 10% is at least 90%. We take our prior distribution to be a beta distribution so that our prior clinical opinion is worth 20% of the weight we will place on the new data. This gives the prior parameters $a = 0.3$, $b = 2.7$. Hence when we make decisions about stopping the study, the data from the study will dominate over the prior opinion.

The following table summarizes the threshold numbers for the stop rule boundary, which would lead to a recommendation to stop the study due to the excess 30-day mortality.

Number of subjects	Stop if the number of deaths within 30 days reaches
2-5	2
6-11	3
12-15	4

We investigated the performance of the above stopping rule by a simulation study. In each simulation run, we generated a study with 15 independent Bernoulli trials, each with a true certain 30-day mortality, and compared these outcomes with the above stopping boundary to determine whether the study was stopped. We repeated the simulation 100,000 times and computed the proportion of stopped studies using the above stopping rule. The following table summarizes the performance of this stopping rule:

True 30-day mortality rate	2.5%	5%	10%	15%	20%	25%	30%	35%
Proportion of Stopped Studies (%)	0.7	3.1	13.8	30.4	48.6	65.5	78.6	88
Average number of subjects (n)	14.9	14.7	13.8	12.5	11	9.5	8.1	6.9
Average number of 30-day mortality (n)	0.4	0.7	1.4	1.9	2.2	2.4	2.4	2.4

These simulation results suggest that our stopping rule has a low probability of stopping a study when the true 30-day mortality rate is 10% or less, and the probability of stopping a study is high when the true 30-day mortality rate exceeds 10%. There, we believe that our stopping rule for 30-day mortality has satisfactory statistical properties.

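### The section 9.4.1 stopping table assumes a boundary check after every subject, but nothing says who makes the check or when, and the death notice omits the DSMB

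*Combined protocol and SAP*

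**What the plan says.** Section 9.4.1 begins with a general commitment: "The study will be monitored to ensure that the mortality within 30-days after the procedure does not substantially exceed an anticipated rate". It then sets a boundary of 2 deaths among 2-5 subjects, 3 among 6-11 and 4 among 12-15, "which would lead to a recommendation to stop the study due to the excess 30-day mortality", and reports its simulated performance. It does not say who compares deaths with the boundary, what prompts the comparison, or whether a subject still inside the 30-day window counts in the number of subjects.

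Section 9.4 says that the DSMB "will monitor the safety of subjects in the study as described in the investigational plan", and then: "The NHLBI DSMB will review the protocol progress report at six month intervals". It adds: "The DSMB may recommend early termination of the study for considerations of safety and efficacy". One kind of event has a stated earlier route: "Unanticipated Adverse Device Effects (UADEs) will be submitted to the DSMB following the same timelines as the IRB".

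Under section 10.2.4 a death is reported to the sponsor within 3 working days and by the sponsor to the NHLBI IRB within 7 days. The DSMB is not named. Section 10.1 lists death among the anticipated device effects. It defines a UADE as a serious effect or death associated with the device that had not already been identified, including in how often it occurs.

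Three other routes exist. After a death or serious UADE, the study is terminated "if the sponsor and the principal investigator determine that the event presents an unreasonable risk to the participating subjects" (section 9.4). Each IRB reviews serious events and "may choose to suspend or terminate the protocol based on those findings" (section 9.4). FDA receives 30-day outcomes after every 5 subjects (section 10.3). None of them mentions the boundary.

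**The concern.** How many subjects are treated, and how many die, before a stop depends on how often the boundary is checked. The table gives the performance of continuous checking, yet the protocol assigns that check to nobody. The DSMB, which section 9.4 allows to recommend termination, is scheduled to meet only every six months and is not on the death notice.

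The boundary counts every death within 30 days. A death attributable to the valve procedure or to other disease counts, but it is not associated with the device and so need not be a UADE. No early route to the DSMB is stated for it.

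The estimated duration is 18 months and follow-up lasts 12. If the first includes the second, accrual takes about 18 - 12 = 6 months, and the first scheduled review could fall after all 15 subjects have been treated. Limiting exposure to a device not previously used in humans is the reason for having the rule, so later stopping is what is at stake.

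**Working it through.** **1. The boundary.** Inputs from section 9.4.1: prior Beta(0.3, 2.7), reference rate 10%, posterior threshold 90%. After d deaths in n subjects the posterior is Beta(0.3 + d, 2.7 + n - d), and the rule stops if P(rate > 0.10) is at least 0.90.

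- n = 5, d = 2: 0.907, stop. n = 6, d = 2: 0.878, so 3 deaths are needed.
- n = 11, d = 3: 0.908, stop. n = 12, d = 3: 0.889, so 4 are needed.
- n = 15, d = 4: 0.943, stop.

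The stated boundary is reproduced exactly.

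**2. The performance table.** Let q(n, d) be the probability of still being open with d deaths after n subjects, at true rate p. Then q(n, d) = (1 - p) q(n-1, d) + p q(n-1, d-1), and at each look the states at or above the threshold are removed. The stop proportion is the total removed. Average subjects is the sum of n times the amount removed at n, plus 15 times what remains. Average deaths equals p times average subjects.

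| True rate | Stated: stop %, subjects, deaths | Check after every subject | Looks at 5, 10, 15 |
|---|---|---|---|
| 10% | 13.8, 13.8, 1.4 | 13.89, 13.84, 1.38 | 12.90, 14.03, 1.40 |
| 20% | 48.6, 11, 2.2 | 48.65, 11.05, 2.21 | 46.73, 11.74, 2.35 |
| 30% | 78.6, 8.1, 2.4 | 78.85, 8.12, 2.43 | 77.54, 9.30, 2.79 |
| 35% | 88, 6.9, 2.4 | 88.18, 6.89, 2.41 | 87.33, 8.25, 2.89 |

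A check after every subject matches all three rows at all eight tabulated rates (stop proportions within 0.3 points). Looks at 5, 10 and 15 come close on stop proportion (largest gap 48.6 - 46.73 = 1.9 points) but miss the subject and death rows. That closeness depends on where the looks fall: looks at 3, 6, 9, 12 and 15 stop 41.5% at 20% and 74.4% at 30%.

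The last column holds accrual until each look is complete. If accrual continues and each look comes 30 days after the 5th, 10th and 15th subject, simulation gives 12.1-12.5 subjects at 20% and 10.0-10.6 at 30%.

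**3. Worst case: the count is compared with the boundary only at six-monthly reviews, and no other route acts.** The documents give no accrual rate. The assumptions are even accrual over 6, 9 or 12 months, deaths spread uniformly over the 30 days, and a DSMB clock starting at the first treated subject. Results come from 40,000 simulated studies per setting; deaths are rate times subjects (for example 0.30 x 12.3 = 3.7).

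| True rate | Stated stop % | 6 months | 9 months | 12 months |
|---|---|---|---|---|
| 10%: stop % | 13.8 | 5.5 | 8.5 | 6.6 |
| 20%: stop %, subjects, deaths | 48.6 | 35.4, 15, 3.0 | 41.0, 13.8, 2.8 | 37.6, 13.8, 2.8 |
| 30%: stop %, subjects, deaths | 78.6 | 70.3, 15, 4.5 | 74.1, 12.7, 3.8 | 72.0, 12.3, 3.7 |

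With 6-month accrual this is a single look at 15 subjects. The exact binomial probability of 4 or more deaths is then 5.6%, 35.2% and 70.3%, which agrees.

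If the review instead reads the deaths in order and asks whether the boundary was ever crossed, the proportion returns to 48-49% at 20% and 79% at 30%. Average subjects are still 13.0-15 and 11.4-15.

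**4. Is a check at each death enough?** The threshold never falls as subjects accumulate (2, then 3, then 4), so adding a survivor cannot create a crossing. A check at each reported death therefore misses none.

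**The case against.** The strongest reply is that prompt action is already possible. The sponsor learns of every death within 3 working days. The termination clause in section 9.4 covers any death, not only UADEs. The IRBs review all serious adverse events, and FDA sees 30-day outcomes every 5 subjects. Thresholds for every count from 2 to 15 suggest that frequent checking was intended. The UADE definition reaches deaths occurring more often than foreseen, so device-associated deaths in excess of the anticipated 10% could reach the DSMB early even though death is on the anticipated list. DSMB monitoring also follows an investigational plan that is not part of this document.

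Much of this stands. A reader might infer from the six-monthly interval that the boundary will in fact wait for a DSMB meeting, that all 15 subjects will be treated before anyone can act, or that no death can reach the DSMB sooner. The documents do not support those readings: section 9.4.1 does not tie the boundary to DSMB meetings, the other routes exist, and accrual time is not stated. Nor is there any ground for calling the boundary or the table miscalculated, since both reproduce.

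The reply does not close the gap. The sponsor and investigator clause is a judgement on each event, and no route instructs anyone to count deaths against the boundary. The opposite inference, that stop proportions hardly depend on the schedule, also fails: it holds for looks at 5, 10 and 15 and for an ordered reading of the record, but not for counts taken at six-monthly reviews.

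**Conclusion.** The concern holds as a gap in assignment and notification, and it should be fixed. The table describes immediate checks after every subject; the protocol neither assigns those checks nor tells the DSMB of a 30-day death that is not a UADE.

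The firm part of the size needs no accrual assumption. At 30% mortality, looks every 5 subjects with accrual held cost about 1.2 more subjects (9.3 against 8.1) and 0.4 more deaths (2.8 against 2.4), with little change in the chance of stopping. The worst case rests on the accrual, death-timing and clock assumptions above and on every other route staying inactive. It gives stop proportions of about 5-9%, 35-41% and 70-74% at 10%, 20% and 30%, and it marks the outer limit rather than the expected result. Confidence is medium, because the investigational plan may already settle the point.

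**What to change.** - In section 9.4.1, state that the existing boundary is checked at each reported 30-day death, for example by the sponsor, who already receives the notice, and that a crossing goes at once to the DSMB for an ad hoc recommendation.
- In section 10.2.4, add the DSMB to the existing death notice.
- Label the performance table as assuming immediate checks after every subject, and say which subjects count in the number of subjects.

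If the investigational plan already provides for this, a cross-reference is enough. The boundary need not change. How enrolment is handled while a recommendation is pending is for the sponsor and DSMB to specify.

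With a 5-day notice lag and subjects 12 to 24 days apart (both assumptions; the spacing is 15 subjects over 6 to 12 months), checks at each death give 8.3-9.4 subjects and 2.5-2.8 deaths at 30% mortality, close to the table.

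The choice of denominator is minor. At a true 10% rate and with no lag, counting only subjects of known status stops 15.7% of studies at 12-day spacing and counting all treated subjects stops 12.2%. At 24-day spacing the figures are 14.5% and 13.4% (stated 13.8%). Either is acceptable if it is stated, and re-running the simulation is optional.

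The cost is a few sentences and one more addressee on a notice that is already sent.
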